10.3 Investigator Site File and Archiving

Upon initiation of the trial, the Investigator will be provided with an Investigator Site File containing all necessary trial documents, which will be completed throughout the trial and updated as necessary. The file must be available for review by the Monitor, during Sponsor audits and for inspection by Health Authorities during and after the trial, and must be safely archived for at least 15 years after the end of the trial.

The documents to be archived include the Subject Identification List and the signed subject Informed Consent Forms. If archiving of the Investigator Site File is no longer possible at the site, the Investigator must notify the Sponsor/designee.

All original subject files (medical records) must be stored at the site (hospital, research institute, or practice) for the longest possible time permitted by the applicable regulations, and/or as per ICH GCP guidelines, whichever is longer. In any case, the Investigator should ensure that no destruction of medical records is performed without the written approval of the Sponsor.

10.4 Monitoring, Quality Assurance and Inspection by Health Authorities

This trial will be monitored in accordance with the ICH GCP and any other applicable regulations. The site Monitor will perform visits to the trial site at regular intervals.

The clinical trial protocol, each step of the data capture procedure, and the handling of the data, including the final clinical trial report, will be subject to independent Quality Assurance activities. Audits may be conducted at any time during or after the trial to ensure the validity and integrity of the trial data. Representatives of the Quality Assurance unit from the Sponsor or a designated organization, as well as Health Authorities, must be permitted to access all trial documents and other materials at the site, including the Investigator Site File, the completed eCRFs, all IMPs and IMP accountability records, and the original medical records or files for each subject.

10.5 Changes to the Clinical Trial Protocol

Changes to the clinical trial protocol will be documented in writing. Substantive amendments will usually require submission to the Health Authorities and to the relevant IEC for approval or favorable opinion. In such cases, the amendment will be implemented only after approval or favorable opinion has been obtained.

Minor (non-substantial) protocol amendments, including administrative changes, will be filed by the Sponsor and at the site. They will be submitted to the relevant IEC or to Health Authorities only where requested by pertinent regulations. Any amendment that could affect the subject's agreement to participate in the trial requires additional informed consent prior to implementation following the process as described in Section 9.2.

10.6 Clinical Trial Report and Publication Policy

10.6.1 Clinical Trial Report

After completion of the trial, a clinical trial report will be written by Nuvisan GmbH following the guidance in ICH Topic E3 [8].

		Screening	Tepotinib alone	Tepotinib with omeprazole fasted	Tepotinib with omeprazole fed	End of Trial Visit	Total	
Clinical laboratory tests								
Biochemistry (incl. viral serology, TSH and FSH levels, if applicable)	4.7	1	3 ^a	3 ^b	3 ^b	1	11	51.7
Hematology	2.7	1	3 ^a	3 ^b	3 ^b	1	11	29.7
PK	2.0		21 ^c	21 ^d	21 ^d		63	126.0
PGx (optional)	2.0		2 ^e				2	4.0
Total		2	29	27	27	2	87	211.4

Note: The number of blood samples may increase above the scheduled number. Blood samples for clinical laboratory follow-up determinations may become necessary. Technical failure of PK/PGx blood drawing may lead the Investigator to decide immediately to repeat a single blood drawing to have a sample.

Maximal blood volume drawn: Estimate per Subject in this Study

that will not be exceeded in this planned trial as by experience of the Investigating Institution:

250

FSH = follicle stimulating hormone, PK = pharmacokinetics; PGx = pharmacogenetics, TSH = thyroid stimulating hormone.

Clinical laboratory (biochemistry and hematology) blood samples:

- a Tepotinib alone: before drug administration on Day -1, before tepotinib administration on Day 1 and before discharge on Day 4 = 3 samples.
- b Tepotinib with omeprazole: Day -1, before tepotinib administration on Day 5, and before discharge on Day 8 = 3 samples.

PK blood samples for determination of tepotinib and its metabolites:

- c Tepotinib alone: predose, 15, 30, 45, 60, 90 min, and 2, 3, 4, 6, 8, 12, 16, 24, 36, 48, 60, 72, 96, 120 and 144 h postdose = 21 samples.
- d Tepotinib with omeprazole: predose, 15, 30, 45, 60, 90 min, and 2, 3, 4, 6, 8, 12, 16, 24, 36, 48, 60, 72, 96, 120 and 144 h postdose = 21 samples.

PGx blood samples:

- e PGx blood samples of 2 x 2 mL (optional) to be drawn on Day -1, in Period 1 only = 2 samples.

Appendix III Contraception Guidance

Definitions

Woman of Childbearing Potential

A woman is considered fertile following menarche and until becoming post-menopausal unless permanently sterile. Permanent sterilization methods include hysterectomy, bilateral salpingectomy, and bilateral oophorectomy.

Women in the following categories are not considered women of childbearing potential

1. Premenopausal female with 1 of the following:

- Documented hysterectomy
- Documented bilateral salpingectomy
- Documented bilateral oophorectomy

Note: Documentation can come from the site personnel's: review of participant's medical records, medical examination, or medical history interview.

2. Premenarchal

3. Postmenopausal female

- Females who are postmenopausal (age-related amenorrhea \geq 12 consecutive months and increased follicle-stimulating hormone [FSH] > 40 mIU/mL), or who have undergone documented hysterectomy, bilateral salpingectomy, or bilateral oophorectomy are exempt from pregnancy testing. If necessary to confirm postmenopausal status, FSH will be re-tested at Screening.
- Females on hormone replacement therapy (HRT) and whose menopausal status is in doubt will be required to use one of the non-hormonal highly effective contraception methods if they wish to continue their HRT during the study. Otherwise, they must discontinue HRT to allow confirmation of postmenopausal status before study enrollment.

Contraceptive Guidance for Women of Childbearing Potential:

Highly Effective Contraceptive Methods That Are User Dependent	
Failure rate of <1% per year when used consistently and correctly.	

Combined (estrogen- and progestogen-containing) hormonal contraception associated with inhibition of ovulation ^b
oralintravaginaltransdermalProgestogen-only hormonal contraception associated with inhibition of ovulation ^b
oralinjectable	
Highly Effective Methods That Are User Independent	

Implantable progestogen-only hormonal contraception associated with inhibition of ovulation ^bIntrauterine device (IUD)Intrauterine hormone-releasing system (IUS)bilateral tubal occlusion	

Vasectomized partner 
(A vasectomized partner is a highly effective contraception method provided that the partner is the sole male sexual partner of the woman of childbearing potential and the absence of sperm has been confirmed. If not, an additional highly effective method of contraception should be used.)
	
NOTES:	

a) Typical use failure rates may differ from those when used consistently and correctly. Use should be consistent with local regulations regarding the use of contraceptive methods for participants participating in clinical studies.
 
b) Hormonal contraception may be susceptible to interaction with the study drug, which may reduce the efficacy of the contraceptive method. In this case another highly effective (not hormone based) method of contraception must be utilized during the treatment period and for at least 3 months after the last dose of study treatment

## List of Abbreviations and Definition of Terms

AE	Adverse Event
AUC 0-t	Area under the plasma concentration-time curve from time zero (= dosing time) to the last sampling time ( $t_{last}$ ) at which the concentration is at or above the lower limit of quantification
AUC 0-∞	Area under the plasma concentration-time curve from time zero (= dosing time) extrapolated to infinity
AUC extra	The AUC from time $t_{last}$ extrapolated to infinity
AUC extra%	AUC extra / AUC 0-∞ × 100
BMI	Body Mass Index
CI	Confidence Interval
CL/f	Apparent total body clearance considering the fraction of dose (f) absorbed
C max	Maximum plasma concentration observed
CSR	Clinical Study Report
CV%	Coefficient of Variation
ECG	Electrocardiogram
eCRF	Electronic Case Report Form
GeoCV%	Geometric Coefficient of Variation
GeoMean	Geometric Mean
IAP	Integrated Analysis Plan
ICH	International Conference on Harmonization
LCI	Lower Confidence Interval
LLOQ	Lower Limit of Quantification
MedDRA	Medical Dictionary for Regulatory Activities
NCI-CTCAE	National Cancer Institute – Common Terminology Criteria for Adverse Events
PD	Pharmacodynamics
PGx	Pharmacogenetics
PK	Pharmacokinetics
PT	Preferred Term

Q1	25th Percentile
Q3	75th Percentile
QTcF	Corrected QT interval per Fridericia's formula
SAE	Serious Adverse Event
SEM	Standard Error of the Mean
SOC	System Organ Class
SD	Standard Deviation
$t_{1/2}$	Terminal half-life
TEAE	Treatment Emergent Adverse Event
$t_{\text{lag}}$	Time prior to the first measurable (non-zero) concentration
$t_{\text{last}}$	The last sampling time at which the concentration is at or above the lower limit of quantification
$t_{\text{max}}$	Time to reach the maximum plasma concentration
ULOQ	Upper Limit of Quantification
UCI	Upper Confidence Interval
Vz/f	Apparent volume of distribution during the terminal phase

### 3 Modification History

Unique Identifier for Version	Date of IAP Version	Author	Changes from the Previous Version
1.0	27-JUL-2018	PI	Original document

### 4 Purpose of the Integrated Analysis Plan

The purpose of this IAP is to document technical and detailed specifications for the final analysis of data collected for protocol MS200095-0039. Results of the analyses described in this IAP will be included in the Clinical Study Report (CSR). Additionally, the planned analyses identified in this IAP will be included in regulatory submissions or future manuscripts. Any post-hoc, or unplanned analyses performed to provide results for inclusion in the CSR but not identified in this prospective IAP will be clearly identified in the CSR.

The IAP is based upon section 8 (Statistics) of the trial protocol and protocol amendments and is prepared in compliance with ICH E9.

## 5

## Objectives and Endpoints

	Objective	Endpoint	IAP section
Primary Objective	To investigate the effect of omeprazole co-administration on the single dose PK of tepotinib under fed conditions in healthy subjects.	PK profile of tepotinib following Treatments A and C in terms of area under the concentration-time curve (AUC) from time zero to the last sampling time 144 h postdose ( $AUC_{0-t}$ ), AUC from time zero extrapolated to infinity ( $AUC_{0-\infty}$ ) and maximum plasma concentration ( $C_{max}$ ).	16.1.1
Secondary Objective	To investigate the effect of food on the single dose PK of tepotinib after co-administration of omeprazole and tepotinib	PK profile of tepotinib following Treatment B in terms of $AUC_{0-t}$ from time zero to 144 h postdose, $AUC_{0-\infty}$ and $C_{max}$ PK profile of tepotinib following Treatments A, B and C in terms of time of the maximum drug concentration ( $t_{max}$ ), terminal half-life ( $t_{1/2}$ ), time prior to the first measurable (non-zero) concentration ( $t_{lag}$ ), apparent total body clearance (CL/f), apparent volume of distribution during terminal phase ( $V_z/f$ )	16.1.2
	To assess the safety and tolerability of tepotinib alone and upon co-administration of omeprazole.	Occurrence of treatment emergent adverse events (TEAEs, incidence, frequency, intensity and causality), occurrence of changes in safety laboratory assessments, 12-lead electrocardiograms (ECGs) and vital signs in subjects receiving tepotinib alone and together with omeprazole assessed from Day -1 of Period 1 until the End of Trial Visit.	15
Exploratory Objective	To investigate the effect of omeprazole co-administration on the PK of metabolites of tepotinib under fed conditions	PK profiles of tepotinib metabolites: $AUC_{0-t}$ , $AUC_{0-\infty}$ , $C_{max}$ , $t_{max}$ , and $t_{1/2}$ Ratios of tepotinib metabolites to tepotinib: $MR_{AUC_{0-\infty}}$ and $MRC_{max}$	16.1.3
	To explore the effect of pharmacogenetics (PGx) and variations of associated genes on the PK profile of tepotinib (if applicable, participation is optional).	Genetic variants and mutations in genes that potentially influence the PK of tepotinib.	16.2

## 6

## Overview of Planned Analyses

All final, planned analyses identified in the Clinical Trial Protocol and in this IAP will be performed only after the last subject has completed the last visit, ie, end of trial visit/early termination visit with all trial data in-house, all data queries resolved, and the database locked.

A data review meeting will be held prior to database lock. In addition, no database can be locked until this IAP has been approved.

## 7

## Changes to the Planned Analyses in the Clinical Trial Protocol

The statistical methods as described in the protocol were adopted.

# 8

## Protocol Deviations and Analysis Sets

### 8.1

#### Definition of Protocol Deviations and Analysis Sets

Important protocol deviations are protocol deviations that might significantly affect the completeness, accuracy, and/or reliability of the study data or that might significantly affect a subject's rights, safety, or well-being.

The following deviations will be identified and confirmed prior to or at the Data Review Meeting at the latest.

Important protocol deviations include

- Deviations from the inclusion and exclusion criteria
- Concomitant medication violations (see Section 6.5.1 of the protocol)
- Use of prohibited medicines (see Section 6.5.2. of the protocol)
- Subjects that receive incorrect treatment or dose
- Sample processing errors that may lead to inaccurate bioanalytical results
- Vomiting or diarrhea following oral dosing (these instances will be discussed on a case-by-case basis)
- Deviation from Good Clinical Practice
- Non-compliance to study procedures or deviations from study procedures likely to affect the primary endpoints (e.g. subject develops withdrawal criteria whilst on the study but is not withdrawn)
- Deviation from study medication compliance in terms of medical conditions and/or AEs that may have interfered with drug disposition or with respect to factors likely to affect the primary endpoints

All important protocol deviations will be documented in CDISC datasets whether identified through sites monitoring or medical review.

## 8.2

### Definition of Analysis Sets and Subgroups

For purposes of analysis, the following populations are defined:

Population	Description
Screening	The screening analysis set will include all subjects who provided signed informed consent, regardless of treatment status in the trial. This set will be used for subject disposition.
Safety	The Safety Analysis Set will include all subjects who have received at least 1 dose of planned IMP and have had 1 subsequent safety assessment. Subjects will be analyzed according to the actual treatment they receive.
Pharmacokinetic	The PK Analysis Set will consist of all subjects who receive at least one dose of IMP, have no clinically important protocol deviations or important events affecting PK, and provide at least one measurable postdose concentration. Subjects will be analyzed according to the actual treatment they received. All PK analyses will be based on this analysis set. Subjects may be excluded after vomiting or following diarrhea in a particular period as this could render the plasma concentration-time profile unreliable. The use of a concomitant medication that might interfere with the PK of any investigational drug could be a reason for excluding a subject.

## 9

### General Specifications for Data Analyses

Statistical analyses will be performed using the computer program package SAS® System for Windows™ (Version 9.4 or later; SAS Institute, Cary, North Carolina, USA).

The results of this trial will be reported using summary tables, figures, and data listings, as appropriate. All data will be summarized by treatment and/or scheduled time point, as appropriate.

For demographic, baseline and safety assessments, continuous measurements will be summarized by means of descriptive statistics (ie, number and percentage of observations, number and percentage of missing observations, mean, standard deviation [SD], median, Q1 and Q3, minimum, and maximum) and categorical data will be summarized by means of frequency tables (ie, count and percentages), if not stated otherwise. Mean, Median, Q1, Q3, Min, Max will have the same precision as the SDTM data (decimal places). SD will be presented with one decimal place more than the mean. For subject disposition and demographic tables the denominator will be the number of subjects in the analysis set. Counts of missing observations will be included as a separate category.

If not otherwise specified, ‘baseline’ refers to the last scheduled measurement before administration of the first drug in each period. However, if a subject is missing the baseline

collection, the previous non-missing evaluation within the same period predose could become the baseline value. If no baseline or previous to baseline evaluations exist then the baseline value will be treated as missing.

The following calculations and derivations, as applicable, will be used:

- Change from baseline: post-baseline visit value - baseline value
- Duration of AE (in days hh:mm) = end date and time - start date and time of the AE, if missing time for either the beginning or end then = end date – start date + 1
- Days hh:mm from dosing = start date and time of the event - date and time dose administration; (for treatment-emergent AEs), if missing time for either the dosing or event then = event start date – date of dose administration + 1
- Rel. Day in study of AE = start date of the event – date of First Admin + 1 (for AEs on or after the day of dosing)
- Rel. Day in study of AE = start date of the event – date of First Admin (for pre-treatment AEs only)

Repeated laboratory assessments will be flagged as repeats in the subject data listings and not included in summary tables statistics (unless the scheduled measurement was considered unreliable, e.g. due to technical reasons, and needed to be replaced by an unscheduled repeat measurement).

In this phase 1 PK study missing observations will be assumed to be missing completely at random (MCAR). No action will be taken to handle missing data. A subject who withdraws prior to the last planned observation in a trial period will be included in the analyses up to the time of discontinuation.

The following treatment labels will be used in listing and tables:

- tepotinib, fed
- tepotinib + omeprazole, fasted
- tepotinib + omeprazole, fed

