5.1 Overall Trial Design and Plan

This is a Phase I, open-label, 3-period, crossover study to investigate the effect of omeprazole on the PK of tepotinib in 12 healthy subjects under fasted and fed condition. A flowchart summarizing the overall study design is shown in [Figure 2](#). Two subjects each will be randomized to one of the six possible treatment sequences.

The study will be divided into 3 periods: in one period, the PK of tepotinib will be evaluated after single dose administration under fed condition (Treatment A), and in two periods omeprazole will be administered for 5 days and a respective single dose of tepotinib will be co-administered on Day 5. Thereby tepotinib will be administered 2 hours after omeprazole administration once under fasted (Treatment B) and once under fed conditions (Treatment C). The washout period will be at least 14 days between tepotinib single dose administrations (see [Figure 2](#)). Subjects will be randomized to one of six possible treatment sequences as detailed in Section 8.2.

Figure 2 Study Design, Exemplified for Sequence 1

Sequence 1	Treatment A				WO ^a	Treatment B				WO ^a	Treatment C					
	Day					Day					Day					
Procedure	-1	1	2 - 4	5 - 7		-1	1 - 4	5	6 - 8	9 - 11		-1	1 - 4	5	6 - 8	9 - 11
Tepotinib administration		↑						↑					↑			
Omeprazole administration						↑↑↑↑↑		↑				↑↑↑↑↑	↑			
PK blood sampling		↔					↔					↔				
Safety assessments ^b	↔				↑		↔				↑		↔			
AE monitoring	↔															
Hospitalization	↔					↔					↔					

Treatment A = tepotinib alone fed; Treatment B = tepotinib fasted with omeprazole; Treatment C = tepotinib fed with omeprazole

a: WO = washout; the washout period will be at least 14 days between tepotinib single dose administrations.

b: Safety assessments: Vital signs, 12-lead ECG, clinical laboratory.

A screening period will occur from Day -21 to Day -2.

Subjects will be admitted to the study site on Day -1 of each period. After administration of tepotinib alone the subjects will be resident at the study site under medical supervision from Days -1 to 4 and must visit the site on the morning of Days 5 to 7 for further blood sampling. In both periods with omeprazole co-administration the subjects will be resident at the study site under medical supervision from Days -1 to 8 and must visit the site on the morning of Days 9 to 11 for further blood sampling.

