8.3.2 Secondary Endpoints

- PK profile of tepotinib following Treatment B in terms of AUC_{0-t} , C_{max} from time zero to 144 h postdose, and $AUC_{0-\infty}$
- PK profile of tepotinib following Treatments A, B and C in terms of time of the maximum drug concentration (t_{max}), terminal half-life ($t_{1/2}$), time prior to the first measurable (non-zero) concentration (t_{lag}), apparent total body clearance (CL/f), and apparent volume of distribution during terminal phase (V_z/f)
- Occurrence of TEAEs (incidence, frequency, intensity and causality), occurrence of changes in safety laboratory assessments, 12-lead ECGs and vital signs in subjects receiving tepotinib alone and together with omeprazole assessed from Day -1 of Period 1 until the End of Trial Visit.

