## **15.3 Clinical Laboratory Evaluation**

All laboratory data will be reported with SI units. Laboratory parameters will be listed by subject and time-point and summarized indicating the treatment at the respective time-point using descriptive statistics for absolute values and change from baseline over time.. Data listings of abnormalities as per the NCI-CTCAE guideline will be provided. Shift tables for laboratory tests will be presented by treatment. Shift tables will be based on NCI-CTCAE grades, where possible, and on normal ranges otherwise. They will be produced for

- End of Trial versus Screening
- Discharge versus Pre-dose (Tepotinib administration) within periods.

Laboratory values that are outside the normal range will also be flagged in the data listings, along with corresponding normal ranges and NCI-CTCAE grade and will additionally be listed separately.

See section 7.4.3 of the clinical study protocol for a table of the safety laboratory evaluations.

Safety laboratory values are separated into:

- Hematology
- Biochemistry
- Urinalysis
- Other tests

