## 15.4                    **Vital Signs**

Vital signs will be listed by subject and time-point and summarized for absolute values and changes-from-baseline by visit and treatment using descriptive statistics. Descriptive statistics tables will start at baseline.

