## 15.5                    **ECG Evaluation**

ECG data will be listed by subject and time-point and summarized by absolute values and changes-from-baseline by treatment group using descriptive statistics. Descriptive statistics tables will start at baseline. Clinically significant ECG findings for individual subjects will be listed and summarized.

The time intervals [PR, QRS, RR, QT and corrected QT intervals [based on Fridericia's formula, QTcF] will be summarized descriptively by treatment.

The Fridericia's Correction (QTcF) is derived as follows:

$$\text{Fridericia's Correction (QTcF)} \quad QTc_f = \frac{QT}{\sqrt[3]{RR}}$$

where: RR = RR-interval measured in seconds.

Observed QTcF values will be categorized according to their absolute values into the categories

- $\leq 430$  ms,
- $> 430$  and  $\leq 450$  ms,
- $> 450$  and  $\leq 480$  ms,
- $> 480$  and  $\leq 500$  ms, and
- $> 500$  ms,

and categorized according to their absolute change from baseline into the categories

- $\leq 30$  ms,
- $> 30$  and  $\leq 60$  ms, and
- $> 60$  ms.

The number and percentage of subjects by these categories at any post-dose assessment will be tabulated by treatment group. All ECG measurements will be listed, with abnormalities indicated.

Investigator reported interpretation results will also be listed and tabulated treatment using the number and percentage of subjects for each interpretation category (Normal, Abnormal Not Clinically Significant [NCS], Abnormal Clinically Significant [CS].

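### The SAP 9 baseline is Day 1 before tepotinib in Treatment A but Day -1 in B and C, so the A and C safety changes are not matched on time to tepotinib

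*SAP*

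**What the plan says.** SAP 9 sets one default: baseline "refers to the last scheduled measurement before administration of the first drug in each period". Change is the later value minus that baseline. Protocol 8.5.4 also plans changes from baseline but does not define baseline.

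The summaries that use the default are:

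- **Vital signs (SAP 15.4):** "Vital signs will be listed by subject and time-point and summarized for absolute values and changes-from-baseline by visit and treatment using descriptive statistics".
- **ECG (SAP 15.5):** "ECG data will be listed by subject and time-point and summarized by absolute values and changes-from-baseline by treatment group using descriptive statistics". QTcF changes are also put into three categories (up to 30 ms, above 30 and up to 60 ms, above 60 ms), with this rule: "The number and percentage of subjects by these categories at any post-dose assessment will be tabulated by treatment group".
- **Laboratory (SAP 15.3):** values are "summarized indicating the treatment at the respective time-point using descriptive statistics for absolute values and change from baseline over time".

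Only the SAP 15.3 laboratory shift tables name other reference points. One is End of Trial against Screening. The other is "Discharge versus Pre-dose (Tepotinib administration) within periods", which is a pre-tepotinib reference in every treatment.

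Changes in laboratory values, ECG and vital signs are a secondary endpoint (Protocol 8.3.2), described as occurring "in subjects receiving tepotinib alone and together with omeprazole assessed from Day -1 of Period 1 until the End of Trial Visit". The food states are given in the Figure 2 legend of Protocol 5.1: "Treatment A = tepotinib alone fed; Treatment B = tepotinib fasted with omeprazole; Treatment C = tepotinib fed with omeprazole".

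**The concern.** The rule reads the same for each period, but it lands on a different day because the first drug differs. In A the baseline lies just before tepotinib. In B and C it lies on admission day, before the omeprazole run-in. A change from baseline after tepotinib in B or C therefore mixes two things: whatever happened from Day -1 to Day 5 (residence and omeprazole), and whatever happened after tepotinib. In A only the second is present.

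The tables are by treatment, and the secondary endpoint concerns tepotinib alone and together with omeprazole, so a reader will set the columns side by side. The natural pair is C and A, both fed; A and B also differ in food state. That reader could take part of the run-in shift for a difference after tepotinib, or miss a difference that the shift hides. The SAP does not mention that the baseline day differs by treatment.

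**Working it through.** **Step 1. Apply the rule to the schedules.** The inputs are SAP 9, Protocol Tables 2 and 3 with footnotes, Protocol 7.1.2 and Appendix II.

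| | Treatment A | Treatments B and C |
|---|---|---|
| First drug of the period | Tepotinib, Day 1 | Omeprazole, Day 1 |
| Laboratory tests | Day -1, Day 1 predose, Day 4 | Day -1, Day 5 pre-tepotinib, Day 8 |
| ECG, blood pressure/pulse | Day -1, Day 1 predose, then 2 to 72 h | Day -1, Day 5 pre-tepotinib, then 2 to 72 h |
| Default baseline | Day 1 predose | Day -1 |

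For Days 1 to 4 of B and C, Protocol 7.1.2 lists only omeprazole dosing and a Day 4 physical examination. Appendix II counts three laboratory samples in those periods, none on Day 1.

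**Step 2. Time from baseline to tepotinib.**

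- A: vital signs and ECG fall within 60 min before dosing. Protocol 7.1.2 puts them before a breakfast that starts 30 min before dosing, so the interval is 30 to 60 min, with no omeprazole.
- B and C: there is no Day 0, so Day -1 to Day 5 is 1 + 4 = 5 days, with 5 omeprazole doses (Days 1 to 5).
- The 72 h assessment is about 3 days after baseline in A and about 5 + 3 = 8 days after it in B and C.

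**Step 3. Split the change in B and C.**

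Change at time t = (Day 5 predose − Day -1) + (value at t − Day 5 predose).

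A has only the second kind of term. C and B share the same baseline rule, so their comparison is unaffected.

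**Step 4. What the planned tables would show.** The by-visit vital sign tables and the over-time laboratory tables would display the mean of the first term. They would not give the SD or quartiles of the second term. The QTcF change categories pool each subject's post-dose ECGs, so that table cannot separate the two terms. The SAP also does not say whether the Day 5 pre-tepotinib ECG, which follows omeprazole, counts as post-dose.

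**Step 5. Illustrate the size for QTcF.** The documents give no size or sign for the shift and no QTcF SDs, so every input here is an assumption: no tepotinib effect; reading = day effect N(0, d) + error N(0, e); a common shift added in B and C from Day 5; seven ECGs (four on the dosing day, one on each of the next three days). The result is 12 × P(largest change > 30 ms), from 1,000,000 draws per setting. The central case is d = 3 and e = 8 ms; the range covers d = 3 and 6 with e = 6, 8 and 10 ms.

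| Setting | Expected subjects of 12 above 30 ms, central | Range |
|---|---|---|
| A | 0.34 | 0.04–1.4 |
| B/C, shift −5 ms | 0.13 | 0.01–0.9 |
| B/C, no shift | 0.42 | 0.06–1.7 |
| B/C, shift +5 ms | 1.08 | 0.3–2.9 |
| B/C, shift +10 ms | 2.35 | 1.0–4.3 |

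- With no shift, the central gap is 0.42 − 0.34 = 0.08. The largest in the grid is 1.73 against 1.42, about 0.3 (d = 6, e = 10).
- In the central case a +5 ms shift gives 1.08 − 0.34 = 0.74 and a +10 ms shift gives 2.35 − 0.34 = 2.01. A −5 ms shift puts B/C below A by 0.34 − 0.13 = 0.21.
- Above 60 ms, the largest expected count in the grid is 0.086 of 12.
- Measured from the pre-tepotinib reading, B/C equals A in this model. That is true by construction, because the model has no food or time-of-day effect.

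**The case against.** The strongest defence is that the rule is coherent. Every baseline precedes all drug in its period, so A, B and C are alike in being untreated at that point, and the change in C describes the omeprazole-plus-tepotinib regimen that the safety objective names. This stands. A reader might infer that the Day -1 baseline is wrong; the documents do not support that, and it should be kept.

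Much is also visible already: mean changes by visit or over time for vital signs and laboratory values, matched within-period laboratory shift tables, absolute QTcF categories, and ECG listings in which 12 subjects can be traced by hand. This stands too. What remains is the QTcF change table and the spread of the change after tepotinib.

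A reader might infer that the plan will inflate QTcF increases in B and C. The documents do not support that either: the shift is unknown, could be negative, and makes little difference if absent. Nor does the point extend to all vital signs. Body temperature is not named in the predose and postdose footnotes of Tables 2 and 3, so it is not established there.

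Finally, the Day 5 reference has limits of its own. It is on omeprazole, so it cannot show an omeprazole effect. In C, breakfast starts 30 min before dosing, so by the nominal schedule 30 of the 60 min of the predose window follow its start, and the protocol does not fix the order. Laboratory samples are specified as fasted (Protocol 7.4.3), so the food limit concerns ECG and blood pressure/pulse. These limits are reasons to add the second reference beside the first, not in its place.

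**Conclusion.** The concern holds in a limited form. For laboratory values, ECG and blood pressure/pulse, the default baseline is a valid whole-regimen reference, but the A and C changes are not matched on time to tepotinib: B and C carry a Day -1 to Day 5 term that A does not. The mismatch follows directly from the SAP rule and the protocol schedules and needs no assumption.

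Its numerical effect does need assumptions. On the SDs in the working, no shift means a gap of at most about 0.3 of 12 subjects above 30 ms. A gap of a whole subject appears only under assumed shifts of +5 to +10 ms, and the count above 60 ms is essentially unaffected throughout.

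The summaries are descriptive and no hypothesis test is planned. PK, C versus B, absolute values and the within-period laboratory shift tables are outside the point. It is a minor improvement to the safety tables.

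**What to change.** In SAP 9 and 15.3 to 15.5:

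- Keep the present baseline, label it whole-regimen change, and name the baseline day by treatment (Day 1 predose in A, Day -1 in B and C).
- Add change from the last scheduled pre-tepotinib value (Day 1 in A, Day 5 in B and C) for ECG including the QTcF change categories, blood pressure/pulse and laboratory values. Use it when A is set beside C.
- Define the post-dose assessments for the QTcF categories as the seven times after tepotinib: 2, 4, 8, 12, 24, 48 and 72 h.
- Footnote the new tables: the Day 5 reference is on omeprazole and shows only the increment after tepotinib; and in C the predose ECG and blood pressure/pulse reading may, by the nominal schedule, fall after breakfast has started. Do not require reporting against actual breakfast time, because the documents do not say that it is recorded.

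The cost is SAP wording, one extra derived baseline and a few descriptive tables from values already scheduled. The downside is a second set of changes that must be read beside the first.
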